Since 1998, the Danish Knee Arthroplasty Register has registered knee replacements (both primary and revisions) performed in Denmark. Traditionally, the most important measure within register research of knee replacements has been the cumulative revision rate, which describes how many patients experience a revision after a given period of time. Around 13% of primary knee arthroplasties are revised for the first time within the first 20 years in Denmark. In the last 20 years, more than 20,000 revisions have been performed. In 2020, 1048 were performed (3).

As the number of performed annual primary procedures increases, so will the number of annual revisions. Upfill-Brown et al. examined the number of revisions in the United States in the period 2012 to 2019. The number of revisions increased by 29.6% per year (4). See **Figure 1**. Kurtz et al. and Pavel et al. have projected, on the basis of large national registries in the USA and England, containing several hundreds of thousands of patients, that the annual number of revisions after primary knee arthroplasty will increase over 300% in England and over 600% in the USA in 2030 compared to the number of revisions in 2005 (2, 5). See **Figure 2**.

Figure 1: Projection of the annual incidence of performed revisions in the United States.

From Uffill-Brown et al.

[figure not shown]
[figure not shown]

Fig. 2

The projected number of revision total hip arthroplasty (THA) and total knee arthroplasty (TKA) procedures in the United States from 2005 to 2030.

Figure 2: Projection of the annual incidence of revisions carried out in England and Wales.

From Patel et al.

Graph showing the projected total number of revision knee arthroplasties in England and Wales between 2013 and 2030.

[figure not shown]
Re-revision

Unfortunately, even after revision, there is a risk of new complications, which may necessitate another revision (re-revision). In some patients, one complication follows another, and these patients may require several revisions. We use the term *multiply revised* when a patient experience at least three revisions of their knee replacement. In principle, there is no upper limit to the number of revisions in a knee, and some knees are revised more than 10 times. Some patients may end with an arthrodesis or amputation (6, 7).

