There is a paucity of studies investigating multiple revised patients. Deere et al. investigated the subject in 2019, containing just over 30,000 patients from the English register NJR(8). The study found that 20% of those revised for the first time were revised a second time after 13 years. 20% of those were revised for the third time after 5 years, and 20% of those were revised again for the fourth time within 3 years. The risk of multiply revisions was higher in men and in younger patients. Also, the study found that the risk of revision increased as time between revisions decreased.

In 2010, Ong et al. investigated the risk of revision after primary and first revision after total knee arthroplasty (TKA) and total hip arthroplasty (9). The study contained data from 73,000 primary knee arthroplasties, and 1600 revisions performed between 1997 and 2006. The study found that the risk of a second revision was 6 times higher than the risk of a first revision. See **Figure 3**:

Figure 3: Graph illustrating risk of revision after primary and first revision. From Ong et al.

In 2021, Belt et al. investigated the association of the indication for revision and the risk of re-revision (10). The study found that the cumulative re-revision rate was 19% after 8 years (significantly higher than the cumulative revision rate after primary knee arthroplasty). Klasan et al. found that the re-revision rate after revision due to aseptic loosening was 12% over a 16-year period (1999-2015) in New Zealand (11). In 2018, Postler et al. examined a smaller population of 300 patients in a prospective, single-centre study (12). The study found that re-revisions were performed 4 years since the last revision, while first revisions were performed after 8 years since primary knee arthroplasty.

A Danish study was performed in 2022, by Arndt et al. which investigated rate of re-revision after revision for either “aseptic resolution” or “pain without resolution” (13). The study included data from 4299 revisions from 1997 to 2018 from the Danish Knee Arthroplasty Register. The study found a cumulative revision rate of 23% after 20 years for patients with pain without loosening. For patients with aseptic loosening, the cumulative revision rate after 20 years was 19%.

No study has investigated the cumulative revision rates stratified by number of previous revisions in a national population. It is not known how many patients live with a revision

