In WP-A1 we want to calculate:

- 1) Annual incidence of revision arthroplasties.

Incidence is calculated as the number of n-grade revisions performed in Denmark during a given year as a proportion of the current year's population. This is done for each level of revision.

The incidence rate is also calculated:

$$IR = \frac{\text{Number of } n\text{-grade revisions}}{\text{Number of person-years in observation period}}$$

- 2) The continuous prevalence of revision knees.

Prevalence is calculated as the number of patients living with n-grade revision knee as a proportion of the current year's population. This is done for each level of revision.

- 3) The relationship between the annual incidence of n-grade revisions with the incidence of primary procedures in the preceding years.

$$\text{rate ratio} = \frac{\text{IR for } n - \text{ grade revision}}{\text{IR for primary procedures the previous year}}$$

WPA2

The analyzes will be based on the population defined in WP-A1. We will estimate the cumulative incidence (risk) for the different levels of revision and examine whether factors such as patient demographics, implant type and other operative technical conditions influence the cumulative incidence.

$$\begin{aligned} & \text{risk for } n - \text{ grade revision} \\ & = \frac{\text{number of } n - \text{ grade revisions in the observation period}}{\text{numbers with } n - 1 \text{ revisions}} \end{aligned}$$

To investigate whether patient demographics, implant type, indication for revision and other operative technical conditions have an effect on the subsequent incidence of revision, we will use regression analysis. It will be relevant to investigate possible confounding of the variables.

In addition, we will create "cumulative incidence plots" for each level of revision to illustrate prosthesis survival.

WPA3

The lifetime risk will be determined as a summation of the expected remaining life based on the CRR for the individual events (primary procedure and n-grade revision). As in WPA2, we will examine whether patient demographics, implant type and other operative technical conditions have an effect on the risk of revision. In addition, the lifetime risk of arthrodesis or amputation as an event will also be calculated. Thus, data from WP-A2 becomes the starting point for the calculations.

Applicant's duties

The applicant's duties consist of:

The overall responsibility for the execution of the project.

Obtaining necessary data approvals.

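### WP-A2's only written risk formula is a crude proportion over a 24-year window, so it does not estimate the time-indexed revision risk by grade and distorts the comparison across grades

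*Protocol*

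**What the plan says.** The Background of the protocol (Size of the problem) treats the cumulative revision rate (CRR) as time-indexed: it "describes how many patients experience a revision after a given period of time". The purpose statement for WP-A2 makes the CRR by number of previous revisions the target, for use in preoperative information.

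The Statistics section (WPA2) then states "We will estimate the cumulative incidence (risk) for the different levels of revision" and writes the risk as a single ratio. The numerator is the count of n-"grade revisions in the observation period"; the denominator is the number with n-1 revisions. The same section adds cumulative incidence plots "for each level of revision to illustrate prosthesis survival" and a regression of unspecified type. On the population it says only: "The analyzes will be based on the population defined in WP-A1".

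WPA3 takes WP-A2 as its starting point and builds lifetime risk from the CRR over expected remaining life. The SAP covers incidence and prevalence only and defines no CRR.

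**The concern.** A proportion over a calendar window equals a risk at a stated time only if everyone is followed for that time. Here a knee operated on in 1998 has up to 24 years of follow-up and one operated on in December 2021 has almost none. A knee must also use up time to reach grade n-1, so follow-up after that procedure shortens as grade rises. Each grade's ratio therefore refers to a different, unstated horizon.

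The comparison by number of previous revisions is the gap that the Background says no national study has filled, and it is the comparison most affected. Preoperative information and the lifetime risks of WP-A3 both depend on it.

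**Working it through.** The documents give no WP-A2 result or event count, so there is no figure of the plan to reproduce. What follows is an illustration.

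**Inputs from the protocol (Background).**
- First revision: "Around 13% of primary knee arthroplasties are revised for the first time within the first 20 years in Denmark".
- Second: "20% of those revised for the first time were revised a second time after 13 years".
- Third: "20% of those were revised for the third time after 5 years".
- Window: 24 years.

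**Assumptions not in the documents.** Time to the n-th revision is Weibull with shape 1 (constant hazard), 0.7 or 0.5 (hazard highest early), scaled to the rates above read as net risks. Annual mortality is 0, 4% or 6%. Entry is flat, or rises linearly from 3,000 to 10,500 a year. That makes 18 settings. The denominator is knees that ever reached n-1.

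**Step 1: first revision, in closed form.** With a constant hazard, λ = −ln(0.87)/20 = 0.00696 per year. With flat entry over T = 24 years and no deaths, the expected ratio is 1 − (1 − e^(−λT))/(λT). Here λT = 0.1671, so the ratio is 1 − 0.1539/0.1671 = 7.9%. Rising entry gives 6.5%. With shape 0.7 the range is 7.6–8.8%, and with shape 0.5 it is 8.6–9.6%. The input was 13% at 20 years. The ratio lies near the 10-year risk (6.7%, 8.2% and 9.4% for the three shapes), but nothing in the formula says so.

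**Step 2: follow-up by grade.** With flat entry and no deaths, mean potential follow-up from the (n-1)th procedure is 12.0, 8.1 and 6.2 years for n = 1, 2, 3 (constant hazard), or 12.0, 9.7 and 8.2 years (shape 0.5).

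**Step 3: equal hazards.** Give every grade the same hazard (20% at 13 years), with flat entry and 4% mortality. With a constant hazard the ratio reads 13.7%, 10.9% and 8.9% for grades 1–3, while the true 10-year risk is 13.1% at each grade. With shape 0.5 it reads 15.4%, 14.5% and 13.7% against 15.8%.

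**Step 4: the cited rates.** The table gives the range over entry and mortality settings. The true value in the second column is 1.

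| Weibull shape | False grade-3 to grade-1 ratio, equal hazards | Third-to-first contrast from the formula | True contrast, 10 years | True contrast, 20 years |
|---|---|---|---|---|
| 1 | about 0.55–0.75 | 2.9–4.0 | 5.4 | 4.5–4.9 |
| 0.7 | 0.71–0.86 | 2.6–3.3 | 3.7 | 3.4–3.6 |
| 0.5 | about 0.82–0.94 | 2.4–2.7 | 2.9 | 2.8 |

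In each of the 18 settings the false ratio was below 1, and the formula's contrast was below the true contrast for that setting at both 10 and 20 years.

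**Step 5: the denominator.** For the third revision (flat entry, no deaths, constant hazard), dividing by knees that ever reached grade 2 gives 22.55%. Dividing by knees still at grade 2 gives 22.55/77.45 = 29.1%, which is an odds.

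**Step 6: hand-over to WP-A3.** Suppose a curve that already treats death as competing is passed on and survival is applied again. With a constant hazard and 4% mortality, lifetime first-revision risk is 0.00696/(0.00696 + 0.04) = 14.8%. Counting mortality twice gives 0.00696/(0.00696 + 0.08) = 8.0%. With shape 0.5 the figures are 12.7% and 9.2%.

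**The case against.** The strongest reply is that the formula is shorthand. The protocol names the quantity a cumulative incidence, describes the CRR as time-indexed, plans curves by grade, and collects dated deaths, disappearances and emigration (Organization of data, table G). Properly estimated curves would give the right answer. That stands, but the ratio is still the only risk definition written down, and no estimator is named for the curves.

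A reader might infer that two contradictory risks per grade will be published, or that the ratio will be used to counsel patients. The documents do not support this: nowhere do they say that the ratio will be reported beside the curves, used for counselling or passed to WP-A3. They leave open which of the two is the CRR.

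A reader might also make much of the denominator. The word risk requires the numerator to be part of the denominator, which favours knees that ever reached n-1. One clarifying phrase is enough.

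On size, several objections stand:
- Hazard shape, mortality and entry are assumed, and with shape 0.5 the distortion is small.
- The rates mix a Danish figure with English register figures, and the 5-year third-revision figure is extended to 10–20 years.
- The equal-hazard case runs against the Background, where risk rises with grade. With the cited rates the ratio still rises, so the direction is not reversed.

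**Conclusion.** The point holds. The written rule is a crude proportion under staggered entry and does not estimate the CRR by grade that the protocol sets as WP-A2's target. It can produce a false decline across grades, and at horizons of 10–20 years it understates a real rise. Under a constant hazard the understatement is material (2.9–4.0 against 4.5–5.4); with shape 0.5 it is slight (2.4–2.7 against 2.8–2.9). These are illustrations resting on the assumptions listed, not estimates for Denmark.

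It would go too far to conclude that WP-A2 cannot deliver the right quantity. Table G should support it and the plots may be meant to show it, so the defect is in the stated method. It should be corrected before WP-A2 is analysed.

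**What to change.** **WP-A2.** Replace the ratio, or relabel it as a crude descriptive proportion over knees that ever reached n-1. Define the CRR as the Aalen-Johansen cumulative incidence of the n-th revision from the date of the (n-1)th procedure, in knees of the primary cohort (PRIM) that reach grade n-1. Then:
- treat death as a competing event;
- censor at emigration, disappearance and 31 December 2021;
- state whether amputation and arthrodesis are competing events or counted revisions, because the protocol puts their codes in the revision cohort, the SAP leaves them out of its study, and WP-A3 treats them as separate events;
- report at stated fixed times with numbers at risk;
- use the same estimator for the plots, and fit the regression as a time-to-event model on the same time scale.

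**WP-A3.** State that lifetime risk uses cause-specific revision hazards combined once with mortality, or one multistate model. The death-competing curves should not have survival applied to them again.

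**Cost.** A few sentences in WP-A2 and WP-A3, and slightly more analysis work. Table G is described as holding the dated events, but exact death dates must be confirmed: SAP section 3 describes only the year of death, and the section 2 table labels the field a year while giving its format as a date.

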- 1) What is the annual incidence of revisions of various degrees, and how has the incidence changed during the last 20 years?
- 2) What is the current prevalence of n-grade revisions, and how has the prevalence changed during the last 20 years?
- 3) What is the relationship between the annual incidence of revisions of n-grade with the incidence of primary procedures in the preceding years?

WP-A2: Cumulative Revision Rates (CRR)

The purpose of this WP is to determine the cumulative revision rate (CRR) for revisions of different grades (number of previous revisions) to generate information that can be used for informing patients preoperatively.

Research questions:

1. What is the CRR for n-grade revision?
2. Is CRR influenced by demographic and surgical variables such as sex, age, education, implant type, place of residence, income, operative technical conditions and the indication of revision such as infection, aseptic loosening, instability, pain without reason?

WP-A3: Lifetime risk of multiple revisions

The purpose of this WP is to determine the lifetime risk of revision of various grades as well as the lifetime risk of arthrodesis and amputation. These risks will be investigated in relation to demographic and surgical variables.

Research questions:

1. What is the lifetime risk that a patient with a given combination of demographic and surgical variables will need n-number of revisions after primary arthroplasty?
2. As above but with arthrodesis and amputation as the risk event.

Review of literature

To gather relevant background information for this protocol, MEDLINE via pubmed was searched to find relevant literature in the field. The MESH words "knee replacement" and "reoperation" were used. We wanted to identify articles that either described epidemiological findings regarding multiple revision knee arthroplasties or described risk factors associated with repeated revisions. There were no MESH words containing "rerevision", "multiply revisions" or "repeated revisions".

Articles found: 4350 results.

Based on the title, this number of abstracts were reviewed: 97

Of the abstracts, so many articles were reviewed and read: 65

Number of articles used in the protocol: 47.

Material and methods

Design

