Landspatientregisteret (LPR) is a national and clinical database administered by the Danish Health Authority since 1976. All information generated when a patient is treated by the public health service is reported here. In addition to information regarding procedures and admissions, the register contains information on residence, partner status, level of education, income, comorbidities and emigration amongst others. Operations are recorded according to the NOMESCO classification, while diagnoses are coded according to the ICD-10 classification.

Identification of primary procedures

We will determine the cohort of primary procedures from DKR (called P-DKR) by identifying all primary procedures performed from January 1st 1998 to December 31st 2021. P-DKR is then transferred to Danmarks Statistik (DS). Through DS, all primary procedures in the observation period will be identified using NOMESCO operation codes (KNGB*) and these will be collected in a cohort called P-SD. P-DKR and P-SD will be joined into a cohort called PRIM and this cohort will best describe all primary procedures performed in Denmark during the observation period.

Identification of revision procedures

The DKR cohort of revisions (R-DKR) will be identified by all registrations marked as revisions during the observation period. R-DKR is also transferred to DS. All revisions will be identified in DS as R-DS using the NOMESCO operation codes KNG* (knee procedure), KNGC* (revision of knee), KNGG* (arthrodesis) and KNFQ19 (femur amputation). The cohorts R-DKR and R-DS will be combined and called REV. This cohort will best describe revision procedures performed in Denmark during the observation period.

Insertion of cement spacers presents a special registration problem, as different registration practices exist. Some use KNGS codes (eg KNGC59A – Insertion of spacer in a knee joint in connection with revision). We intend to not consider spacer insertion as a revision. For example a two-stage revision will be considered as one revision.

Organization of data

A table (G) with PRIM and REV will be created. G will contain information on revisions, deaths, disappearances, emigration and the associated dates. For each knee joint in PRIM and for each date in the observation period, it will be possible to describe the status of the knee joint.

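### WP-A2 pools each revision grade over the preceding interval; if short intervals carry higher risk, the fixed 2021 end biases cumulative incidence plots for second and later revisions upward, mainly beyond 10 years

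*Protocol*

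**What the plan says.** The protocol's WP-A2 purpose is to estimate a cumulative revision rate (CRR) for each grade, "to generate information that can be used for informing patients preoperatively". Under Statistics, WPA2, the plan reads: "We will estimate the cumulative incidence (risk) for the different levels of revision and examine whether factors such as patient demographics, implant type" (among others) influence it. That section gives two estimators. The first is a ratio whose numerator is the count of n-"grade revisions in the observation period" and whose denominator is the number with n−1 revisions. The second is a set of cumulative incidence plots "for each level of revision to illustrate prosthesis survival", with no estimator named.

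The factors to be examined are listed in the WP-A2 research questions as "variables such as sex, age, education, implant type, place of residence, income, operative technical conditions and the indication of revision". The Statistics section repeats the same kind of list. The interval since the preceding operation is in neither. In the Background (Re-revision), however, the protocol reports from a cited registry study that "the study found that the risk of revision increased as time between revisions decreased".

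The cohort is built by "identifying all primary procedures performed from January 1st 1998 to December 31st 2021", and revisions are taken from the same window. Table G (Organization of data) holds revisions, deaths and emigration with their dates, so the interval can be derived. The SAP covers only incidence and prevalence and adds no CRR method.

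**The concern.** Follow-up after a first revision equals 24 years minus the calendar time of the primary minus the first interval. Knees that failed early can be followed for long; knees that failed late are cut off soon. If the interval also predicts the next failure, censoring is related to risk. Kaplan-Meier and Aalen-Johansen curves both assume that it is not. At long times a pooled curve then rests almost entirely on knees that failed early.

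Two things are at stake. The late part of the curves for second and later revision would be overstated, and WP-A3 takes the WP-A2 results as its starting point for lifetime risk. A single figure per grade would also give the same risk to a patient revised at six months and one revised at 15 years, which sits poorly with the aim of informing patients.

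**Working it through.** The documents give no CRR result for WP-A2 and no hazard ratio for the interval, so there is no planned figure to reproduce. The size has to come from a model with stated assumptions.

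**From the documents**
- Window: 1 January 1998 to 31 December 2021, 24 years.
- First revision: about 13% at 20 years (Size of the problem).
- Second revision: 20% at 13 years (cited study, Re-revision).

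**Assumed**
- Primaries uniform over the window; no deaths.
- First-revision hazard 1.5% per year for 2 years, then 0.62%. Check: 1 − exp(−(0.03 + 18 × 0.0062)) = 1 − exp(−0.1416) = 13.2% at 20 years.
- Second interval Weibull, shape 0.6, scaled to 20% at 13 years over all knees first revised within 24 years of the primary.
- Hazard ratios for a first interval <1 year and 1–5 years against 5+ years: 1.5/1.2, 2.0/1.4 or 3.0/1.8, with 1/1 as control.

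**Formulas**
- Let f(u) be the density of the first interval. The weight of interval stratum g still under potential follow-up at time t after first revision is w_g(t) = ∫_g f(u) · max(24 − u − t, 0) du.
- Pooled hazard at t = Σ w_g(t) S_g(t) h_g(t) / Σ w_g(t) S_g(t), where S_g and h_g are the stratum's survival and hazard. The pooled curve is 1 − exp(−∫ pooled hazard).
- Truth in the same knees (first revised inside the window) = Σ w_g(0) F_g(t) / Σ w_g(0), with F_g = 1 − S_g.
- Written ratio = expected second revisions inside the window / knees first revised inside the window.

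**Results by numerical integration (%)**

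| Hazard ratios | Pooled, 10 y | True, 10 y | Excess | Pooled, 20 y | True, 20 y | Excess | Written ratio |
|---|---|---|---|---|---|---|---|
| 1 / 1 | 17.4 | 17.4 | 0 | 25.1 | 25.1 | 0 | 14.9 |
| 1.5 / 1.2 | 18.5 | 18.2 | 0.3 | 27.4 | 26.3 | 1.1 | 15.9 |
| 2.0 / 1.4 | 19.5 | 18.9 | 0.6 | 29.2 | 27.2 | 2.0 | 16.7 |
| 3.0 / 1.8 | 21.0 | 20.1 | 0.9 | 32.0 | 28.6 | 3.4 | 18.1 |

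Simulating the same model (6 million knees) gave an excess of 0.4 to 1.0 points at 10 years and 1.3 to 3.3 at 20, which agrees to within about 0.2 points.

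**Why the tail is worst.** Knees with a first interval of 5+ years are 49.5% of first-revised knees at the start. In the middle scenario they are about 31% of those at risk at 10 years. At 20 years they are 0%. That last figure needs no hazard ratio: 24 − 20 = 4, so no knee first revised more than 4 years after its primary can be followed for 20 years.

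**What one figure hides.** In the middle scenario the true 10-year risks are 28%, 20% and 15% for first intervals of <1, 1–5 and 5+ years.

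**Sensitivity.** A second simulation let the hazard ratio between intervals of ≤1 and ≥10 years be 2, 4 or 8, with flat or rising accrual and a death rate of 0 or 4% per year. The pooled second-revision excess was 0.4–1.2 points at 10 years and 0.9–5.3 at 20. For third revision it was 0.4–1.6 at 10 years. Stratifying by preceding interval and standardising brought the second-revision curve to within about 0.3 points of the truth at 13 years.

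**The case against.** **The written estimator errs the other way.** A reader might infer that all WP-A2 rates will be too high. The documents do not support that. The ratio in the Statistics section has no time axis and counts recently revised knees as event-free. In the three dependent scenarios it gives 15.9–18.1% against true 20-year risks of 26.3–28.6%. This stands in full: the upward bias belongs to the plots only, and only if they are pooled time-to-event curves.

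**A larger bias could be claimed by changing the target.** Against all knees revised within 24 years of their primary, including those revised after 2021, the true 10-year risk is 17.4% and the pooled 18.5–21.0% looks 1.1 to 3.6 points too high. Most of that gap reflects which knees enter the data, not censoring. The natural target is knees that reached the earlier grade inside the window, so the smaller excess is the one to quote.

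**The interval effect is borrowed.** It is one cited study's qualitative finding, not a Danish estimate, and without it the bias is nil. This also stands.

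**The interval is not excluded.** Both factor lists are open-ended, the dates are held, and confounding is to be investigated. It is fair to say only that the interval is not named. A marginal CRR per grade is also a legitimate estimand that answers the first WP-A2 research question; the weakness is the unhandled dependence, not pooling as such.

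**No 20-year re-revision figure is promised.** True, and only about 5% of first-revised knees could have that much follow-up under the assumed accrual. But no horizon is set for the plots either, so nothing stops the curves from being drawn that far.

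**Conclusion.** The point holds in a limited form. If the plots are pooled time-to-event curves and successive intervals are dependent, the curves for second and later revisions are biased upward. For second revision the excess is about 1 point or less at 10 years and roughly 1 to 3.5 points at 20 years under hazard ratios of 1.5 to 3. Those ratios, the accrual pattern and the hazard shapes are assumptions. The 4-year limit on 20-year follow-up is plain arithmetic on the window.

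The documents do not support saying that the CRRs as a whole are overstated, that the interval has been ruled out, or that the SAP is at fault. Replacing the crude ratio comes first. The change is still worth making, because it uses dates already held, removes nearly all of the bias at 10 to 13 years in the models tried, and gives patients figures that reflect a predictor the protocol itself cites.

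**What to change.** Amend the protocol's WP-A2 statistics text, or write it into a separate SAP for WP-A2:

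- Replace the crude ratio with a cumulative incidence estimate on time since the last operation, with death as a competing event, and name the estimator for the plots.
- For second and later revisions, add curves by preceding interval (for example <1, 1–5 and 5+ years), each stopped where its own follow-up ends.
- Where one figure per grade is kept, standardise the stratum curves to the interval distribution of knees that reached the preceding grade inside the window. Report it only to a horizon that all strata support, about 10 years.
- Include the preceding interval as a covariate in the regression.

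The cost is some protocol wording and a few extra curves. The price in information is shorter horizons, and wider confidence intervals for late-failing strata at high grades.

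### The WP-A3 lifetime-risk rule starts from WP-A2, whose only printed risk formula ignores unequal follow-up and competing death, and it does not say how the revision grades are chained

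*Protocol*

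**What the plan says.** The lifetime-risk method is one sentence in Protocol, Statistics, WPA3: "The lifetime risk will be determined as a summation of the expected remaining life based on the CRR for the individual events", those events being the primary procedure and each grade of revision. The paragraph ends by saying that "data from WP-A2 becomes the starting point for the calculations".

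WPA2 announces its target as follows: "We will estimate the cumulative incidence (risk) for the different levels of revision". It prints one formula. The numerator is the number of n-"grade revisions in the observation period"; the denominator is the number with n-1 revisions. There is no time index, person-time, censoring or death term. WPA2 also plans cumulative incidence plots for each level of revision, without naming an estimator.

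Two other places bear on the reading. The Background (Size of the problem) describes "the cumulative revision rate, which describes how many patients experience a revision after a given period of time". Under Organization of data, "G will contain information on revisions, deaths, disappearances, emigration and the associated dates".

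The research question for WP-A3 asks for the lifetime risk of needing n revisions after primary arthroplasty, by demographic and surgical variables, and the same for arthrodesis and amputation. The SAP covers annual incidence and prevalence only and adds nothing on lifetime risk.

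**The concern.** Primaries enter from January 1998 to December 2021, so follow-up at the end of the window ranges from almost nothing to 24 years. In the WP-A2 formula a knee operated on in late 2021 counts in the denominator exactly like one from 1998. Such a ratio describes the window, not a patient's remaining life. The shortfall grows with remaining life, so it is largest in younger patients, and comparisons between age groups are distorted too.

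A time-indexed curve removes the follow-up problem, but the plan does not say that death competes with revision, nor how emigration is handled. Moreover, a patient can reach grade n only by passing through every earlier grade while alive, and the rule does not say how those steps are joined.

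Lifetime risk is the whole output of the third study. One stated purpose of the project is to give patients realistic expectations when they undergo knee replacement.

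**Working it through.** The documents state no lifetime risk, so there is no figure of the plan's own to reproduce. The check compares what different readings of the rule would return with the quantity wanted.

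**Inputs from the protocol.** First revision: 13% at 20 years (Background, Size of the problem). Second revision: 20% at 13 years; third: 20% at 5 years; fourth: 20% at 3 years (Background, Re-revision, from the cited English register study). Window: 24 years.

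**Assumptions not in the documents.** The percentages are net risks (death removed). Entry is uniform over the window. Mortality is Gompertz with slope 0.1 per year, scaled to a mean remaining life L of 10 to 30 years (10 to 20 after a revision). The revision hazard is constant; for first revision a decreasing Weibull hazard (shape 0.7) is also tried.

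**Hazards.** λ = −ln(1 − p)/t:
- first: −ln(0.87)/20 = 0.00696 per year
- second: −ln(0.80)/13 = 0.0172
- third: −ln(0.80)/5 = 0.0446
- fourth: −ln(0.80)/3 = 0.0744

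**Quantities compared**, with S(t) the survival of the patient:
- Lifetime risk with death competing: ∫ λ·exp(−λt)·S(t) dt over all remaining life.
- Crude WP-A2 ratio: the same integral stopped at the end of 2021, averaged over entry dates.
- Time-indexed net curve read at expected remaining life: 1 − exp(−λL).
- Yearly rates summed over expected remaining life: λL.

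**First revision, constant hazard**

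| L (years) | Crude ratio | Lifetime risk | Crude / lifetime | Net curve at L |
|---|---|---|---|---|
| 10 | 4.8% | 6.6% | 72% | 6.7% |
| 15 | 6.1% | 9.8% | 62% | 9.9% |
| 20 | 6.8% | 12.8% | 53% | 13.0% |
| 25 | 7.3% | 15.8% | 46% | 16.0% |
| 30 | 7.5% | 18.6% | 40% | 18.9% |

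With the Weibull hazard, lifetime risk runs from 7.8% to 16.5%, and the crude ratio recovers 79% falling to 51% of it. The net curve at L is at most about 0.4 points high under either hazard. If the crude ratio is first spread over the window and then summed over L, the result is lower still: 4.8%/24 × 10 = 2.0% at L = 10, and 7.5%/24 × 30 = 9.4% at L = 30.

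**Later grades, each conditional on the grade before (L = 10, 15, 20)**

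| Grade | Crude ratio | Lifetime risk | Net curve at L | Summed rates λL |
|---|---|---|---|---|
| Second | 11.2, 14.0, 15.7% | 15.3, 22.0, 28.2% | 15.8, 22.7, 29.1% | 17, 26, 34% |
| Third | 25.6, 31.1, 34.3% | 33.7, 45.7, 55.5% | 36.0, 48.8, 59.0% | 45, 67, 89% |
| Fourth | 37.4, 44.4, 48.2% | 47.7, 61.5, 71.6% | 52.5, 67.2, 77.4% | 74, 112, 149% |

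For fourth revision the net curve at L is 4.8, 5.7 and 5.8 points too high. The reason is that the net curve bends downward: its value at the mean remaining life exceeds its average over the actual spread of remaining lives. The gap is small when the hazard is low and grows with the hazard, so it is largest in multiply revised knees.

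**Chaining.** As a simple illustration, assume constant mortality of 4% a year, so that each step has probability λ/(λ + 0.04). The steps are 0.148, 0.300 and 0.527. Third revision is then 53% for a knee that has had its second, but 0.148 × 0.300 × 0.527 = 2.3% from primary. The WP-A3 question asks for the second kind of figure; the WP-A2 quantities are of the first kind.

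**The case against.** The strongest reply is that WPA3 names the CRR, not the WP-A2 ratio. The Background places the CRR on a time axis, the planned plots need one, and table G holds the dates. On that reading the input to WPA3 is a curve. This stands: the crude ratio is the literal reading of the one printed formula, not the only possible one. The protocol never says which is meant.

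A reader might go further than the documents allow in three ways.
- That the plan cannot yield a lifetime risk at all. This is not supported: on the time-indexed reading the rule is nearly right for first revision.
- That death is left out. It is not: mortality enters through expected remaining life, and dated deaths are collected. What is missing is its treatment as a competing event.
- That risks are to be added across grades. The sentence sums over remaining life for the individual events; the rule for combining grades is unstated rather than stated wrongly.

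The size is also open to challenge, because the mortality and hazard shapes are assumed. The crude-ratio shortfall had the same direction in every scenario tried; only its size moved.

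None of this supplies an estimator. For later grades the charitable reading is still biased upward, and nothing in the SAP fills the gap.

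**Conclusion.** The point holds, and is more than missing detail. On the literal reading, WP-A3 rests on a proportion that recovers 72% falling to 40% of first-revision lifetime risk as mean remaining life goes from 10 to 30 years (79% to 51% with a decreasing hazard), and summing yearly rates gives impossible values for fourth revision (112% at 15 years, 149% at 20). On the time-indexed reading, first revision is sound to within about 0.4 points, while fourth revision is about 5 to 6 points too high. On neither reading does the rule give the risk of n revisions counted from primary.

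These sizes rest on uniform entry, the assumed mortality, the assumed hazard shapes, and the quoted percentages being net risks. They should be read as indicative. The change should be made before the third study is analysed.

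**What to change.** Replace the WPA3 sentence with a time-indexed estimator built on the dated revisions, deaths and emigration in table G:
- Use a multistate model with death as an absorbing competing state and emigration as censoring.
- Give each reported grade its own state, without pooling at three or more, and include arthrodesis and amputation as events.
- Let transition intensities depend on age, sex and time since the last operation. The Background cites a finding that revision risk rose as the interval between revisions shortened, so age alone is not enough. Enter the WP-A3 surgical variables as covariates or strata.
- Report the probability of ever reaching grade n from primary, with intervals clustered on patient because one patient can contribute two knees.
- State the life-table extrapolation beyond 24 years as an assumption, with a sensitivity range.

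In WPA2, name the estimator behind the cumulative incidence plots, and say that this, not the crude ratio, feeds WPA3.

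The cost is protocol wording, more analysis work on data already planned for table G, and national life tables. The downside is that results beyond 24 years will rest on extrapolation assumptions, which must be shown.
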